7 MEASUREMENTS OF TREATMENT COMPLIANCE

Due to the method of administration of the treatments, compliance will be examined in terms of completed injections. Treatment compliance will be calculated as:

$$\frac{\text{Total number of actual (completed) injections}}{\text{Total number of expected injections}} \times 100\%$$

The total number of expected injections is derived relative to when the study participant finishes treatment. If a study participant completes treatment, four injections are expected during the Double-Blind Treatment Period and nine during the Maintenance Period. A total of thirteen injections are then expected (at Baseline, and at each study visits from Week 4 until Week 48). If a study participant discontinues early, then the number of expected injections is based on the time of early discontinuation relative to the dosing visits.

A summary of percent treatment compliance categorized as <75% and $\geq 75\%$ will be provided by treatment group, as well as a by-study participant listing of treatment compliance.

Compliance will be summarized on the SS for the Double-Blind Period, on the MS for the Maintenance Period and on the SS for the overall period.

Injections missed due to COVID-19 will be summarized and tracked in the listings.

8 EFFICACY ANALYSES

8.1 Statistical analysis of the primary efficacy variable

8.1.1 Derivation of ASAS40 response

The rules described in Section 4.2.1.1 will be followed in the derivation of the ASAS40 response. The ASAS40 response at Week 16 is the primary efficacy variable. The ASAS40 response is defined as:

- an improvement of at least 40%, and
- absolute improvement of at least 2 units on a 0 to 10 numeric rating scale (NRS) in at least 3 of the 4 following domains:
 - Patient's Global Assessment of Disease Activity (PGADA)
 - Pain assessment (total spinal pain, question 1 from total and nocturnal spinal pain)
 - Physical function (measured by the Bath Ankylosing Spondylitis Functional Index (BASFI))
 - Inflammation (represented by the mean of the Bath Ankylosing Spondylitis Disease Activity Index (BASDAI) questions 5 and 6) concerning morning stiffness intensity and duration)

- and no worsening at all in the remaining domain.

8.1.1.1 Derivation of the patient's global assessment of disease activity (PGADA)

Study participants will score the global assessment of their disease activity in answering the following “How active was your spondylitis on average during the last week?” using a NRS where 0 is “not active” and 10 is “very active”.

8.1.1.2 Derivation of the pain assessment domain

The pain assessment domain will correspond to the total spinal pain and will be measured by the study participant in answering the following question “How much pain of your spine due to spondylitis do you have?”. To answer the question, the study participant will consider the average amount of pain in the preceding week and use a NRS ranging from 0 to 10, where 0 represents “no pain” and 10 represents “most severe pain”.

8.1.1.3 Derivation of the physical function domain of the Bath Ankylosing Spondylitis Functional Index (BASFI)

The BASFI contains 10 questions and will be measured by the study participant for assessing their physical functions during the past week. The first 8 questions evaluate activities related to functional anatomical limitations due to the course of AS. The final 2 questions evaluate the study participants’ ability to cope with everyday life. An NRS ranging from 0 (“Easy”) to 10 (“Impossible”) will be used to answer the questions on the test. The arithmetic mean of the 10 scores gives the BASFI score, which is a value between 0 and 10, with lower scores indicating better physical function.

In case of missing answers to 1 or 2 of the single items within the BASFI questionnaire, the BASFI score will be calculated by imputing missing items with the mean of the completed items. Then, the BASFI score will be calculated as described above. If more than 2 of the items are missing, the BASFI score will be left missing.

8.1.1.4 Derivation of the inflammation domain (mean of questions 5 and 6 of the BASDAI)

The BASDAI consists of 6 horizontal NRSs and will be used to measure the disease activity of ankylosing spondylitis from the study participant’s perspective. Each NRS contains 10 units to measure the severity of the 5 major symptoms: fatigue, spinal pain, peripheral joint pain and swelling, enthesitis, and morning stiffness (both severity and duration) over the last week.

The ASAS inflammation component is calculated as the average of the two scores relating to morning stiffness measurements (ie, question 5: “How would you describe the overall level of morning stiffness you have had from the time you wake up?” and question 6: “How long does your morning stiffness last from the time you wake up?”). The ASAS inflammation score ranges from 0 to 10.

If one of the two morning stiffness measurements is missing, the other one will be used as ASAS inflammation score.

If more than one measurement is missing, the ASAS inflammation score will be set to missing.

8.1.2 Primary analysis of the primary efficacy variable

The primary efficacy variable (ASAS40 response at Week 16) will be analyzed for all study participants in the RS.

The primary efficacy analysis will evaluate the composite estimand (NRI) that combines the clinically meaningful improvement from Baseline in ASAS40 response at Week 16 and the intercurrent event of not discontinuing early from study treatment for any reason prior to Week 16.

Note that only **permanent** discontinuations are considered as intercurrent events. This definition is applicable to all analyses defined in this SAP.

The following 4 attributes describe the composite estimand that will be used to define the treatment effect of interest for the primary efficacy analysis:

- Population = Study participants enrolled according to the protocol-specified inclusion/exclusion criteria and randomized to IMP
- Study participant-level outcome = ASAS40 at Week 16
- Intercurrent event handling = An intercurrent event is defined as discontinuation of study treatment prior to Week 16. A composite strategy will be implemented in which a positive clinical outcome is defined as achieving ASAS40 at Week 16 and not discontinuing study treatment through Week 16.
- Population-level summary measure = Conditional odds ratio comparing bimekizumab to placebo.

Intercurrent events will then be acknowledged as an unfavorable outcome for the composite estimand in considering study participants with intercurrent events as ‘non-responders’ to the study treatment.

Consequently, if the date of an intercurrent event (as defined in Section 3.4) occurred prior to or at Week 16, study participants will be considered as “non-responders” at Week 16.

Additionally, missing data at Week 16 that are not preceded by an intercurrent event will be imputed as non-responders.

As outlined in Section 4.5, the statistical null hypothesis for the ASAS40 response at Week 16 is that there is no difference in the proportion of study participants with ASAS40 response between the bimekizumab treatment and placebo (ie, the conditional odds ratio for ASAS40 response in the bimekizumab treatment compared with placebo is equal to 1). The alternative hypothesis is that there is a difference between bimekizumab treatment and placebo.

A logistic regression model will be used to assess the treatment effect on ASAS40 response at Week 16. The model will include fixed effects for treatment, and prior TNF α inhibitor exposure and region as stratification factors. The suitability of including these variables in the model will be assessed using the Hosmer-Lemeshow goodness-of-fit test.

Also, as mentioned in Section 4.1, if the logistic regression model is unable to converge the stratification factors may be dropped to facilitate the model convergence.

The SAS[®] PROC LOGISTIC will be used to run the logistic regression.

The summary table results will present the number of responders, adjusted responder rates and associated 95% CI for bimekizumab and placebo, the adjusted odds ratio and 95% CI for the comparison bimekizumab versus placebo, and the p-value that the OR=1. The treatment comparison will be made using the 2-sided Wald test at a significance level of $\alpha=0.05$.

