4 STATISTICAL/ANALYTICAL ISSUES

4.1 Adjustments for covariates

The primary efficacy analysis that will investigate the treatment effect will be adjusted for:

- Prior TNF α inhibitor exposure (yes, no), and
- Region (Asia, Eastern Europe, North America, Western Europe)

However, prior TNF α inhibitor exposure may be dropped from the model in order to achieve model convergence (ie, in case the likelihood maximization algorithm failed to converge). If convergence is still not obtained, then region may instead or also be dropped from the model. This will be decided at the time of the table creation and clarified in respective table footnotes. Finally, in the case of the continuous secondary endpoints of the testing hierarchy, if the

reference-based multiple imputation model still does not converge, the analysis will be replaced using LOCF as imputation method (see Section 4.2.1.11)

Prior TNF α inhibitor exposure and region are the stratification factors of the randomization. In the event that a study participant is stratified in the incorrect stratum (ie, the stratum recorded in the Interactive voice or web Response System (IXRS) differs from the actual stratum the study participant belongs to), the actual stratum will be used for the analysis.

The secondary analyses will be adjusted on the same categorical factors as the primary analysis. For continuous variables, Baseline value (of the variable of interest) will also be included as covariate where appropriate.

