One indicator variable (region1) will be defined as 0 for regions other than North America and 1 for North America. Two more indicator variables (region2 and region3) will be defined similarly replacing North America with Eastern Europe and Western Europe respectively. In the VAR statement of the imputation model, the indicator variables will be ordered as follows: region1 region2 and region3. In the eventuality that two regions required to be pooled due to a low percentage of study participants randomized in one region (see Section 3.8), the indicator variables defined above will be revised accordingly.

- One indicator variable will be defined for the prior TNF α inhibitor exposure stratification variable: will be coded as 1 for yes and 0 for No.

To maintain consistency with the MCMC method for intermittent missing values, these indicator variables will also be used in the monotone regression step for monotone missing values and treated as continuous variables.

- Step 3: For each of the 100 complete imputed data set obtained from Step 2, the binary responder variable will be derived. In practice, the value at the week of interest (eg, Week 16) in the imputed data sets will be used to categorize the study participant as a responder or not. If study participants have a treatment discontinuation due to AE or lack of efficacy, then the endpoint will be changed to “non-response” for all visits after the IE date.
- Step 4:
 - For secondary efficacy endpoints: For each of the datasets obtained in Step 3, the responder rate will be analyzed using a logistic regression model with factors of treatment group, region, and prior TNF α inhibitor exposure as fixed effects. The suitability of including region and prior TNF α inhibitor exposure at Baseline as fixed effects will be assessed using goodness-of-fit tests (Deviance and Pearson’s and Hosmer-Lemeshow) and added if appropriate and allows model convergence.
 - For other efficacy binary endpoints: At each timepoint, the mean proportion of the responders and 95% CIs will be calculated from the imputed datasets using SAS® PROC MIANALYZE.

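### The only remedy for a failed logistic fit is dropping covariates, which cannot handle an arm with no responders, so the fixed sequence could stop at ASAS partial remission

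*SAP*

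**What the plan says.** Section 8.1.2 fits a logistic model to ASAS40 with treatment, prior TNF inhibitor exposure and region, and states: "The treatment comparison will be made using the 2-sided Wald test". Section 8.2.2 carries the same model to the secondary binary endpoints. Section 4.5 allows each test only after the one before it has rejected.

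The remedy for a failed fit is in two places. Section 8.1.2 says "if the logistic regression model is unable to converge the stratification factors may be dropped to facilitate the model convergence". Section 4.1 names TNF exposure as the first factor to go and adds "If convergence is still not obtained, then region may instead or also be dropped from the model", then "This will be decided at the time of the table creation and clarified in respective table footnotes". Section 3.8 also pools regions that hold less than 10% of randomised participants. The SAP names no penalised, exact or likelihood-ratio method for a binary endpoint.

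On whether the factors belong in the model, Section 4.1 is firm: "The primary efficacy analysis that will investigate the treatment effect will be adjusted for" TNF exposure and region. Section 8.1.2 then says "The suitability of including these variables in the model will be assessed using the Hosmer-Lemeshow goodness-of-fit test", with no threshold and no consequence. Step 4 of Section 4.2.1.4.1, on the supportive multiple-imputation analyses, says that the factors will be assessed by fit tests "and added if appropriate and allows model convergence". Section 4.2.1.4.2 applies that step to composite endpoints such as ASAS40, while Section 8.1.4.4 says that analysis uses the primary model.

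**The concern.** Maximum-likelihood logistic regression has no finite treatment estimate when one arm has no responders. The estimate and its standard error both grow with each iteration, and the Wald statistic shrinks towards zero however large the true difference is. The separation is by treatment, so removing TNF exposure or region leaves it in place. The planned remedy therefore does not address this failure.

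A fixed sequence makes this matter. A p-value near 1 on one rare-response endpoint closes every later test, and a rule written after the codes are known would not be credible. ASAS-PR, with a planned placebo rate of 3.3%, is the exposed endpoint.

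The minor point concerns model specification. Hosmer-Lemeshow is a calibration test and does not show whether a randomisation factor should be kept. With one section firm, one silent on action and one conditional, two programmers could fit different models and both claim to follow the SAP.

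**Working it through.** **Inputs.** 200 bimekizumab and 100 placebo, two-sided 0.05 (Section 2.4). ASAS40 40% vs 15% (2.4.1). ASAS-PR 17% vs 3.3%, stated power 94%; TNF-naive ASAS40 48% vs 18%, with 70% naive (2.4.2). ASAS5/6 44% vs 5% (2.4.2).

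**1. The plan's own figures.** The Fleiss continuity-corrected sample-size formula, solved for power at 100 placebo with 2:1 allocation, gives 94.2% for ASAS-PR (stated 94%) and 99.6% for ASAS40 (stated >99%). Both reproduce.

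**2. Chance of no placebo responder, (1 − p)^100.**
- ASAS-PR: 0.967^100 = 3.5%
- ASAS5/6: 0.95^100 = 0.6%
- ASAS40: 0.85^100 = 9 × 10⁻⁸

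**3. The planned Wald test at 34/200 (17%) vs 0/100.** The log odds ratio contains ln(0/100) and its variance contains 1/0, so the printed result depends on where the iterations stop: log OR 14.7, SE 338, p = 0.965 at step 14; log OR 17.7, SE 1513, p = 0.991 at step 17. With expected counts over two TNF strata and four equal regions (an assumption), p is 0.990 for the full model, 0.991 with TNF dropped, 0.990 with region dropped and 0.991 with both dropped.

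**4. The same table with methods that tolerate the cell.**
- Firth, treatment only (0.5 added to each cell): ln[(34.5/166.5)/(0.5/100.5)] = 3.73; SE = √(1/34.5 + 1/166.5 + 1/0.5 + 1/100.5) = 1.43; Wald p = 0.009. With both factors kept, p = 0.007.
- Fisher exact: p = 8 × 10⁻⁷.

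**5. Exact rejection probability.** All outcomes of Bin(200, p₁) × Bin(100, p₀) were enumerated with a treatment-only model, counting the maximum-likelihood Wald test as non-significant at a zero cell.

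| p₁ vs p₀ | Wald as planned | Firth-Wald at a zero cell |
|---|---|---|
| 17% vs 3.3% | 93.5% | 97.0% |
| 17% vs 2% | 86.2% | 99.5% |
| 17% vs 5% | 87.2% | 87.8% |
| 2% vs 2% (null) | 1.0% | 1.1% |
| 3.3% vs 3.3% (null) | 2.2% | 2.2% |
| 10% vs 10% (null) | 4.3% | 4.3% |
| 17% vs 17% (null) | 4.7% | 4.7% |

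At the planned rates, 3.5 of the 6.5 points short of 100% come from zero cells alone.

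**6. Minor point.** The planning rates imply TNF-experienced ASAS40 rates of (0.40 − 0.7 × 0.48)/0.3 = 21.3% and (0.15 − 0.7 × 0.18)/0.3 = 8.0%. A logistic fit to the expected counts gives a treatment OR of 3.99 (95% CI 2.13 to 7.49) with TNF exposure and 3.78 (2.04 to 7.01) without. The gap is ln(3.99/3.78) = 0.055 on the log scale, about 0.17 of the 0.32 standard error. In simulation (3,000 trials per scenario, region effects assumed, 5% level assumed), Hosmer-Lemeshow flagged the full model in 0.8 to 1.2% of trials. It flagged the model without TNF in 0.3 to 0.5%, although the TNF term was significant in 97 to 98%.

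**The case against.** **The primary endpoint is safe.** This stands. A zero placebo cell on ASAS40 is practically impossible and power exceeds 99%. The problem belongs to ASAS-PR and, weakly, to ASAS5/6.

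**No stated figure is missed.** This also stands. The 93.5% already counts every zero cell as a failure and agrees with the stated 94%. The 97.0% is an avoidable loss recovered. It does not show that the plan falls short of its claim, and Type I error is not inflated.

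**The discretion is narrow.** Largely right. Section 4.1 gives a trigger, a first factor to drop and mandatory footnotes. Section 3.8 pools small regions. Section 3.1 puts the SAS output for every hierarchy test into the study report. What stays open is whether region goes in place of TNF exposure or in addition to it. That this would be settled unblinded is inferred from Section 4.3.1, which releases treatment codes at the Week 24 freeze.

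**Firth with a Wald test is conservative.** True for smaller effects: against 0/100, 15/200 gives p = 0.0504 (Fisher 0.003) and 12/200 gives 0.074 (Fisher 0.010). At the planned 17% it recovers the same power as a Fisher or likelihood-ratio fallback. A likelihood-ratio fallback reaches 7.0% Type I error at a common rate of 2%.

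**Two stronger readings are not supported.** A reader might take the Hosmer-Lemeshow sentence as a rule that removes factors from the primary model. Section 8.1.2 states no such action and says the factors are included. A reader might also contrast the binary endpoints with the continuous ones, for which Section 4.1 says that if the "reference-based multiple imputation model still does not converge, the analysis will be replaced using LOCF as imputation method". That replaces a failed imputation model, as Section 4.2.1.11 confirms. It is no fallback for the ANCOVA, so the comparison proves nothing.

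**Conclusion.** The main point holds for the binary key secondary endpoints. The plan's only remedy for a failed logistic fit cannot resolve separation by treatment, and at the planned ASAS-PR rates there is a 3.5% chance that this stops the sequence despite a large effect. The loss depends on the true placebo rate: 13.3 points of power at 2% (99.5 − 86.2), 3.5 at 3.3% and 0.6 at 5%. The enumeration uses a treatment-only model.

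Which endpoints would be lost depends on Figure 4-1, which is not shown in the copy reviewed. If it follows the order of Section 2.4.2, they are ASDAS-MI, ASAS5/6, BASFI, nocturnal spinal pain, ASQoL and SF-36 PCS.

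The fit-test wording is a minor inconsistency. It bears on which conditional odds ratio is reported, by about 0.17 SE. The primary null hypothesis, power and likely conclusion are unaffected. The change should be made, but it is not critical to the trial.

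**What to change.** **Sections 4.1, 8.1.2 and 8.2.2.** Before treatment codes are released, state one ordered fallback for the logistic models and remove the choice left to table creation:
1. Pool regions as in Section 3.8.
2. If an arm has no responders or only responders, or quasi-separation is detected, fit the model by Firth's penalised likelihood with treatment, TNF exposure and region kept. Use the Wald test already named, and footnote the result.
3. If factors must still be dropped for some other failure, give one fixed order.

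Note in the text that Firth-Wald held Type I error at or below 4.7% over the common rates checked (2 to 17%) and is conservative for smaller effects.

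**Sections 8.1.2 and 4.2.1.4.1.** State that treatment, prior TNF exposure and region are kept regardless of fit tests, which are descriptive only. This also brings Step 4 into line with Section 8.1.4.4.

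**Cost.** SAP wording, and a penalised estimate to footnote in the rare case that needs it. Data, sample size and timing do not change.

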8.1.3 Secondary analyses of the primary efficacy variable

Subgroup analyses will be performed on the primary efficacy variable on the RS.

The variables for subgroup analyses are defined in Section 4.8.

Unless otherwise notified, for each subgroup analysis, a logistic regression will be fitted involving the same terms from the primary analysis model and additional terms for the subgroup and the subgroup by treatment interaction. However, for the analysis by stratification variables (ie, prior TNF α exposure and region), the analysis model will contain the same terms from the primary analysis model plus the subgroup by treatment interaction only.

The same imputation method as the one used for the primary analysis (ie, NRI) will be used to handle missing data. The covariates will be provided in the same order as for the primary analysis model with the terms for subgroup and for subgroup by treatment interaction added at the end of the model statement.

For each subgroup category and each treatment group, the number of responders, and adjusted responder rate with associated 95% CI, and the adjusted OR (for the comparison bimekizumab and placebo) and the 95% CI will be provided. Results obtained for each subgroup will be presented in one single table. The ORs and associated 95% CIs for each subgroup category will also be displayed on a single forest-plot.

8.1.4 Supportive analyses of the primary efficacy variable

The following sections described the different supportive analyses planned for the primary efficacy endpoint. Unless otherwise specified:

- the same model as the one specified for the primary analysis will be used
- and the same statistic results as the ones produced for the primary efficacy analysis will be calculated

The adjusted odds ratios and 95% CI for the comparison of bimekizumab versus placebo obtained from the primary analysis and from the supportive analyses described in Section 8.1.4.1, Section 8.1.4.2, and Section 8.1.4.4 to 8.1.4.8 will be displayed on a forest-plot.

8.1.4.1 Analysis on the PPS

The primary analysis described in Section 8.1.2 will be repeated based on the PPS to evaluate the effect of important protocol deviations and protocol-permitted decrease in dosing or dosing frequency of axSpA background medication (due to intolerance/AE/side-effects) on the analysis.

8.1.4.2 Analysis on the FAS

The primary analysis described in Section 8.1.2 will be repeated on the FAS to evaluate whether there are differences in the efficacy analysis between randomized study participants and randomized study participants with a valid Baseline. This analysis will only be produced if the number of study participants in the RS and FAS differs.

